---

## VERSION HISTORY

Version 1.0, 16 November 2017
Initial creation
Version 2.0, 20 July 2018
The language of pre-treatment and post-treatment was changed to pre-dose and post-dose, respectively, as applicable, for consistency throughout the protocol.
Section 1.1 (Schedule of Activities [text and Table 2 {timing for assessments of survival status, hematology, clinical chemistry, and TSH}], Section 1.2 (Synopsis [Progression during treatment, Follow-up of patients post discontinuation of study drug, and Survival]), Section 2.3.2.2 (Risks), Section 4.3.1 (Durvalumab dose rationale), Section 6.7.1 (Durvalumab), Section 7.1.1 (Procedures for discontinuation of study treatment), Section 8.2.3 (Vital signs), and Section 8.3.2 (Time period and frequency for collecting AE and SAE information) were updated to align with the updated content and language in the durvalumab template Edition 1.0.
Table 1 was updated with the definition for End of Treatment as included in footnote “c,” and all subsequent footnotes were updated accordingly from “d” to “u.”
The language of PBMCs was updated to “Whole blood – exploratory analysis (mandatory)” in Tables 1 and 2, and the corresponding footnotes in Tables 1 and 2 were updated accordingly.
The timing of the PRO assessments in Table 2 was updated.
Section 1.2 (Synopsis) was updated with the correct estimated date for last patient completed.
Section 1.2 (Synopsis) was modified to reflect the changes in Section 3 (Objectives and Endpoints), Section 4.1 (Overall design), and Section 9.4 (Statistical Considerations).
Section 1.2 (Synopsis), Section 4.1 (Overall design), and Section 9.2 (Sample size determination) were updated to reflect the change in the number of patients randomized from approximately 256 to 150 patients and the change in the stratification factors to include the patient’s homologous recombination repair (HRR) status (mutant versus wildtype).

Section 1.3 (Schema) was updated to reflect the change in the study design, specifically with regard to the number of patients screened and randomized and the stratification factors.

Section 2.1 (Study rationale) and Section 2.3.4 (Olaparib and durvalumab benefit/risk) were updated to reflect the change in the focus of the endpoints from the HRR mutant to the Full Analysis Set all-comers population.


Section 3 (Objectives and Endpoints) was updated to reflect the revised study objectives and endpoints in light of the change in the analysis plan to analyse the Full Analysis Set as the primary analysis population rather than the HRR mutant subgroup population.

Section 5.1 (Inclusion criteria [criterion number 6]) was updated to reflect the definition of platinum ineligibility.

Section 5.4 (Screen failures) was updated with the removal of the following text: “HRRwt patients excluded from study randomization as part of the biomarker enrichment procedure may not be rescreened” to reflect the revised randomization and stratification process for the study.

Section 6.4.1 (Procedures for randomization) and Section 6.4.2 (Patient enrollment and randomization) were updated to reflect the revised randomization and stratification process for the study.

Section 6.4.4 (Methods for ensuring blinding) and Section 6.4.5 (Methods for unblinding study) were updated with the removal of text concerning the patients, Investigators, and sites remaining blinded to HRR status.

Section 8.1.2 (Tumor biopsies) was updated to provide clarity concerning the genetic testing results.

Section 8.2.1 (Clinical safety laboratory assessments [Table 10]): Text was removed regarding the absolute percentage count.

Section 8.2.6 (Vulnerability Elders Survey-13) was added to include an additional assessment, and Table 1, Section 8.1.4, Section 8.1.4.4, and Section 9.4.2.1 were updated accordingly.

Section 8.5.3 (Storage and destruction of PK/ADA samples) was updated to include revised language concerning the destruction of durvalumab pharmacokinetic (PK) and anti-drug antibody samples and to include information regarding the handling of olaparib PK samples.

Section 8.7 (Genetics) was updated to include subsections 8.7.1 (Optional exploratory genetic sample) and 8.7.2 (Storage and destruction of genetic sample) that discuss the optional exploratory genetic sample and the storage and destruction of the genetic samples.

Section 8.8.1.3 (Collection of whole blood [mandatory]) was updated for clarity of the sample collection.

Section 9 (Statistical Considerations), Section 9.4.2 (Efficacy analyses), Section 9.4.3 (Safety analyses), and Section 9.4.9 (Exploratory analyses) were updated to reflect the changes made in Section 3 (Objectives and Endpoints).


Section 9.4.1.2 (Calculation or derivation of safety variables) was updated to reflect the changes made in Section 1.1 (Schedule of Activities [Table 2]) and in Section 8.3.2 (Time period and frequency for collecting AE and SAE information).

Section 9.4.1.4 (Calculation or derivation of biomarker variables) was updated to include the revised text concerning the determination of PD-L1 status for clarity.

Version 3.0, 15 November 2019

Appendix G was removed due to the TMG update. According to new template, the TMG will be submitted as standalone annex. Appendix G was removed as reference throughout the protocol.

Section 2.3.2.2 updates made per Durvalumab IB edition 15

Section 8.3.13 updates made per Durvalumab IB edition 15 – AESI list and revised wording including changes in relation to removal of Appendix G

Section 8.4.5.1 updates made in language in relation to applying the TMG as separate clinical document

Appendix B2 added language on malignancies,

PFS will not be updated at the time of the final OS analysis for the HRRm subgroup. Change made through the protocol.

Version 4.0, 9 July 2021

Section 2.2.1 Removal of reference to durvalumab being approved in second-line patients with locally advanced/metastatic urothelial cancer.

Section 2.2.2 Removal of reference to durvalumab being approved in US as a treatment for patients with urothelial carcinoma and replacement with text that durvalumab is licensed as a treatment for patients with certain types of lung cancer.
Section 2.2.3 Update on olaparib indications as per olaparib IB edition 20.
Section 2.3.2.1 Removal of reference to durvalumab being approved in US as a treatment for patients with urothelial carcinoma.
Section 4.3.1.3 Removal of reference to durvalumab being approved in US as a treatment for patients with urothelial carcinoma.
Section 4.4.1 Addition of alternative options of treatment supply to subjects in case olaparib or durvalumab are commercially available.
Section 5.3 Table 4 Update to the examples of brand names of contraceptive drugs, to be in line with olaparib IB Edition 20.
Section 8.3.13.2 Text on AESIs for olaparib updated to reflect that MDS/AML was changed to be an important identified risk to be in line with olaparib IB Edition 20.

This Clinical Study Protocol has been subject to a peer review according to AstraZeneca Standard procedures. The Clinical Study Protocol is publicly registered and the results are disclosed and/or published according to the AstraZeneca Global Policy on Bioethics and in compliance with prevailing laws and regulations.

## 1. PROTOCOL SUMMARY

### 1.1 Schedule of Activities (SoA)

The procedures for the screening and treatment period in this study are presented in [Table 1](#), and the procedures for the period following discontinuation of all study treatment are presented in [Table 2](#). Patients who continue beyond Cycle 13 will continue with all Cycle 13 assessments until termination of treatment (see [Table 1](#)).

Whenever vital signs and blood draws are scheduled for the same nominal time, the assessments should occur in the following order: vital signs and then blood draws. The timing of the vital signs assessments should be such that it allows the blood draw (eg, pharmacokinetics [PK] blood sample) to occur at the timepoints indicated in the SoAs. Whenever electrocardiograms (ECGs), vital signs, and blood draws are scheduled for the same nominal time, the assessments should occur in the following order: ECG, vital signs, and then blood draws. The timing of the first 2 assessments should be such that it allows the blood draw (eg, PK blood sample) to occur at the timepoints indicated in the SoAs.

#### For both treatment arms

- Patient-reported outcome (PRO) assessments will be done at the beginning of the dosing cycle regardless of dosing delays. In case of dose delay, PRO assessments may also be assessed during all ad hoc unscheduled visits. Tumor efficacy (Response Evaluation Criteria in Solid Tumors, version 1.1 [RECIST 1.1]) assessment dates are not affected by dose delays and remain as originally scheduled, as they are based on the date of randomization (not the date of therapy).
- All other scheduled assessments must be performed relative to the start of the dosing cycle such that all laboratory procedures, etc., required for dosing should be performed within 3 days prior to dosing.

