**Table 1 Schedule of assessments for patients who are receiving study treatment**

	Screening	C1 a	C2 a	C3 a	C4 a	C5 to PD a,b	EOT visit c	For details, see Section	
Week	-4 to -1	0	q4w ±3 days unless dosing needs to be held for toxicity reasons						
Day	-28 to -1	1	q28days ±3 days unless dosing needs to be held for toxicity reasons						
Pharmacokinetics									
Durvalumab PK sample (serum)		X n	X o		X o			8.5.1.1	
Olaparib PK sample (plasma)		X o	X o		X o			8.5.1.2	
Monitoring									
WHO/ECOG performance status	X	X	X	X	X	X	X	8.2.5	
AE/SAE assessment p	<----->								8.3
Drug accountability		X	All visits						6.3
IP administration									
Durvalumab q		X r	X r	X r	X r	X r		6.1.1.1	
Olaparib/placebo q		X	X	X	X	X		6.1.1.2	
Other assessments and assays									
Tumor biopsy (FFPE sample) s	X s					X s		8.1.2, 8.8.1.1	
Genetic sample	X							8.7, Appendix D	
Durvalumab immunogenicity assessment (ADA sampling to identify ADA responses in patient circulation)		X o	X o		X o			8.5.2	
Whole blood for gene expression (PaxGene-RNA tubes)	X o	X o	X o			X o		8.8.1.2	
Whole blood – exploratory analysis (mandatory) t	X	X	X	X	X	X	X	8.8.1.3	
Urine (mutational analysis)	X	X	X	X	X	X	X	8.8.1.4	
ctDNA (plasma)	X	X	X	X	X	X	X	8.8.1.5	
EORTC QLQ-C30 and EQ-5D-5L u		X	q4w (±7 days relative to Cycle 1 Dose 1 date) until treatment discontinuation						8.1.4.1, 8.1.4.2

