- u PRO assessments will be done using a site-based electronic device at the beginning of the dosing cycle regardless of dosing delays. In case of dose delay, PROs may also be assessed during all ad hoc unscheduled visits. It is preferred that PRO questionnaires are completed prior to any other study procedures (following informed consent) and before discussion of disease progression to avoid biasing the patient's responses to the questions.

Note: All assessments on treatment days are to be performed prior to infusion, unless otherwise indicated.

ADA Antidrug antibody; AE Adverse event; aPTT Activated partial thromboplastin time; BP blood pressure; C Cycle; CR Complete response; CT Computerized tomography; ECG Electrocardiogram; ECOG Eastern Cooperative Oncology Group; eCRF Electronic case report form; EDTA Ethylenediaminetetraacetic acid; EORTC QLQ-C30 European Organisation for Research and Treatment of Cancer 30-item core quality of life questionnaire; EOT End of treatment; EQ-5D-5L EuroQoL 5-dimension, 5-level health state utility index; FFPE Formalin-fixed paraffin-embedded; HBV Hepatitis B virus; HCV Hepatitis C virus; HIV Human immunodeficiency virus; IM Intramuscular; IO Immuno-oncology; IP Investigational product; INR International normalized ratio; IV Intravenous; LFT Liver function test; MRI Magnetic resonance imaging; PD Progressive disease; PGIC Patient Global Impression of Change; PK Pharmacokinetic(s); PR Partial response; PRO Patient-reported outcome; q4w Every 4 weeks; q8w Every 8 weeks; q12w Every 12 weeks; q28days Every 28 days; RECIST 1.1 Response Evaluation Criteria in Solid Tumors, version 1.1; SAE Serious adverse event; T3 Triiodothyronine; T4 Thyroxine; TNM Classification of Malignant Tumors (Tumor, Lymph Nodes, Metastasis); TSH Thyroid stimulating hormone; VES-13 Vulnerability Elders Survey-13; WHO World Health Organization.

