#### **EORTC QLQ-C30**

The EORTC QLQ-C30 consists of 30 questions that can be combined to produce 5 function scales (physical, role, cognitive, emotional, and social), 3 symptom scales (fatigue, pain, and nausea/vomiting), and a global measure of health status. The EORTC QLQ-C30 will be scored according to the EORTC QLQ-C30 scoring manual ([Fayers et al 2001](#)). An outcome variable consisting of a

score from 0 to 100 will be derived for each of the symptom scales, each of the function scales, and the global health status scale in the EORTC QLQ-C30 according to the EORTC QLQ-C30 scoring manual. Higher scores on the global health status and function scales indicate better health status/function, but higher scores on symptom scales represent greater symptom severity.

Definition of clinically meaningful changes

Changes in score compared with baseline will be evaluated. A minimum clinically meaningful change is defined as an absolute change of  $\geq 10$  in the score from baseline for scales from the EORTC QLQ-C30 (Osoba et al 1998). For example, a clinically meaningful improvement in physical function (as assessed by EORTC QLQ-C30) is defined as an increase of  $\geq 10$  in the score from baseline, whereas a clinically meaningful deterioration is defined as a decrease of  $\geq 10$  in the score from baseline. At each post-baseline assessment, the change in symptoms/ functioning from baseline will be categorized as improvement, no change, or deterioration as shown in Table 16. A patient’s best overall response in symptoms, function, or global health status/QoL will be derived as the best response the patient achieved, based on evaluable PRO data collected during the study period. Additional details will be provided in the SAP.

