#### Time to symptom deterioration

For each of the symptoms scales in the EORTC QLQ-C30, time to symptom deterioration will be defined as the time from randomization until the date of the first clinically meaningful symptom deterioration (an increase of  $\geq 10$  in the score from baseline) or death (by any cause) in the absence of a clinically meaningful symptom deterioration, regardless of whether the patient discontinues study treatment or receives another anticancer therapy prior to symptom deterioration. Death will be included as an event only if the death occurs within 2 visits of the last PRO assessment where the symptom change could be evaluated.

Patients whose symptoms (as measured by EORTC QLQ-C30) have not shown a clinically meaningful deterioration and who are alive at the time of the analysis will be censored at the time of their last PRO assessment where the symptom could be evaluated. Also, if symptoms deteriorate after 2 or more missed PRO assessment visits or the patient dies after 2 or more missed PRO assessment visits, the patient will be censored at the time of the last PRO assessment where the symptom could be evaluated. If a patient has no evaluable visits or does not have baseline data they will be censored at Day 0. The population for the analysis of time to symptom deterioration will include a subset of the FAS who have baseline scores of  $\leq 90$ .

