#### Time to health-related quality of life/function deterioration

For global health status/QoL, time to deterioration will be defined as the time from the date of randomization until the date of the first clinically meaningful deterioration (a decrease of  $\geq 10$  in the function scales or the global health status/QoL from baseline) or death (by any cause) in the absence of a clinically meaningful deterioration, regardless of whether the patient discontinues study treatment or receives another anticancer therapy prior to global health status/QoL or functional deterioration. Death will be included as an event only if the death occurs within 2 visits of the last PRO assessment where the global health status/QoL or functional change could be evaluated.

Patients whose HRQoL or function (as measured by EORTC QLQ-C30) have not shown a clinically meaningful deterioration and who are alive at the time of the analysis will be censored at the time of their last PRO assessment where the HRQoL/function could be evaluated. Also, if HRQoL/function deteriorates after 2 or more missed PRO assessment visits or the patient dies after 2 or more

missed PRO assessment visits, the patient will be censored at the time of the last PRO assessment where HRQoL/function could be evaluated. If a patient has no evaluable visits or does not have baseline data they will be censored at Day 0. The population for the analysis of time to HRQoL/function deterioration will include a subset of the FAS who have baseline scores of  $\geq 10$ .

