#### Symptom improvement rate

The symptom improvement rate will be defined as the number (%) of patients with 2 consecutive assessments at least 14 days apart that show a clinically meaningful improvement (a decrease from baseline score  $\geq 10$  for EORTC QLQ-C30 symptom scales) in that symptom from baseline. The denominator will consist of a subset of the FAS who have a baseline symptom score  $\geq 10$ .

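### Extra PRO questionnaires are tied to dose delays while time to deterioration takes the first unconfirmed worsening, so unequal delays between arms can bias the comparison

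*Protocol*

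**What the plan says.** **Collection.** Table 1 schedules QLQ-C30 on treatment "q4w (±7 days relative to Cycle 1 Dose 1 date) until treatment discontinuation", the same in both arms. Section 1.1 (For both treatment arms) keeps that timing whether or not dosing is delayed, then adds one route to further questionnaires: "In case of dose delay, PRO assessments may also be assessed during all ad hoc unscheduled visits". Table 1 footnote u repeats it: "In case of dose delay, PROs may also be assessed during all ad hoc unscheduled visits". No other provision adds on-treatment forms. In the same bullet of Section 1.1, tumor assessment dates are protected from dose delays.

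**Definition.** Section 9.4.1.3 says: "At each post-baseline assessment, the change in symptoms/ functioning from baseline will be categorized as improvement, no change, or deterioration". For symptom scales, "time to symptom deterioration will be defined as the time from randomization until the date of the first clinically meaningful symptom deterioration", meaning a rise of at least 10 points, or death subject to stated limits. For function and global health status, time runs "until the date of the first clinically meaningful deterioration", a fall of at least 10 points. Neither definition asks for confirmation or mentions unscheduled forms. The improvement rate, by contrast, needs "2 consecutive assessments at least 14 days apart".

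**Analysis.** Section 9.4.2.7 compares time to deterioration between arms with a log-rank test stratified as for PFS. Table 3 names global health status, physical function, fatigue and pain as secondary PRO endpoints.

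**The concern.** A time-to-first-event endpoint read from a fluctuating score depends on how often the score is read. More readings give more chances of crossing a 10-point threshold, and earlier ones. Here the number of readings depends on dose delay, which occurs after randomisation and is often caused by toxicity.

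There is reason to expect an imbalance. Only one arm receives olaparib. Section 2.3.4 reports Grade 3 or higher anemia in 39.5% and lymphopenia in 13.2% of patients on the combination in small cell lung cancer. Section 8.4.5.2 manages hematological toxicity with repeatable interruptions of up to 4 weeks, and prolonged ones bring weekly blood counts, each a natural occasion for an ad hoc visit. At stake is a secondary PRO comparison that could tilt against the arm with more delays for reasons unrelated to how patients feel.

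**Working it through.** The protocol gives no power, event count or effect size for time to PRO deterioration, so there is no figure of its own to reproduce. The check is a simulation in which both arms have the same symptom process and differ only in how often delays trigger extra forms.

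**Taken from the protocol**
- Assessments every 4 weeks.
- Event: first rise of at least 10 points, unconfirmed.
- Baseline score of 90 or below, as Section 9.4.1.3 requires for symptom scales.
- 75 patients per arm, used for the type I error runs.

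**Assumed, because the protocol gives no values**
- Delay probability per cycle: 15% in both arms, 15% vs 5%, or 30% vs 10%.
- 1 or 3 extra forms per delay.
- Within-patient SD of 8 or 12 points.
- Correlation over 4 weeks of 0.2, 0.5 or 0.8 (0.8 with SD 8 only).
- Median time under assessment of 3 months, up to 52 weeks.
- Drift of 0.5 points per 4 weeks.
- Scores rounded to steps of 100/9 on the 0–100 scale.
- Delays unrelated to the score; deaths not modelled.

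**Model.** Score = patient mean + weekly AR(1) deviation + drift, with weekly autocorrelation equal to the 4-week correlation to the power 1/4. Hazard ratio = exp(U/V), where U is the log-rank observed minus expected events and V its variance, with 200,000 patients per arm. Each row gives the range over five SD and correlation settings.

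| Delays per cycle | Extra forms per delay | Assessments per patient (approx.) | HR, all forms | HR, scheduled only |
|---|---|---|---|---|
| 15% vs 15% | 3 | 5.5 vs 5.5 | 0.992–1.005 | 0.991–1.000 |
| 15% vs 5% | 1 | 4.5 vs 4.1 | 1.021–1.033 | 0.992–1.004 |
| 15% vs 5% | 3 | 5.5 vs 4.5 | 1.024–1.060 | 0.994–1.000 |
| 30% vs 10% | 1 | 5.1 vs 4.3 | 1.030–1.053 | 0.996–1.009 |
| 30% vs 10% | 3 | 7.1 vs 5.0 | 1.072–1.113 | 0.995–1.005 |

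The equal-delay row shows simulation noise of about 0.01. Every unequal-delay scenario lies above it, always against the arm with more delays. Counting only scheduled assessments returns the ratio to 1 within that noise.

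In the last row, the deterioration-free proportion at week 16 is 1.9 to 3.4 percentage points lower in the arm with more delays (for example 0.495 vs 0.514, and 0.272 vs 0.306). The median is 3 to 4 weeks shorter in three of the five settings and unchanged in two.

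**Type I error.** 3,000 trials of 75 per arm, SD 8, correlation 0.2, 3 extra forms per delay:
- 15% delays in both arms, all forms: 5.0%.
- 30% vs 10%, all forms: 6.8%.
- 30% vs 10%, scheduled forms only: 5.3%.

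The Monte Carlo standard error near 5% is √(0.05 × 0.95 / 3000) = 0.4 percentage points, so 6.8% is a real but modest excess.

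**The case against.** **This belongs in the SAP.** Visit windows and unscheduled forms are commonly settled there, and Section 9.4.1.3 defers further PRO detail to it. A SAP not shown may already restrict the analysis. That stands as far as the missing window rule goes. It does not dispose of the point, because the protocol itself states both the delay-triggered collection and the unconfirmed first-event definition, and the two work badly together.

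**The protocol never says unscheduled PROs count.** Correct. Section 9.4.1.1 says expressly that all RECIST assessments count, scheduled or not; there is no such sentence for PROs. Table 16 speaks of visit responses, and the censoring rules of missed visits. Inclusion follows from classifying each post-baseline assessment and taking the first worsening, with nothing to exclude ad hoc forms. That is the literal reading, not an explicit rule.

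**A reader might infer that the experimental arm deteriorates earlier by construction.** The documents do not support that. The forms are optional, sites are blinded to olaparib or placebo, and the bias needs both use of the option and unequal delays. No delay rate is given for either arm. The anemia figure comes from another tumor type, and Section 2.3.4 reports no comparator with it. Table 1 also defines its cycles by durvalumab, which both arms receive, so it is not fully clear that interrupting olaparib/placebo alone triggers the option, although Section 1.1 uses the word delay for that treatment too. Blinding does not remove the concern, since delay itself can depend on treatment.

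**A reader might also infer a larger effect.** Letting scores shift by up to 10 points during a delay gives event-rate ratios up to 1.23. Part of that is genuine worsening detected sooner, so it is not a measure of artefact.

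**Low consequence.** Sections 9.1 and 9.4.10 carry alpha only through PFS and OS, and Section 9.4.2.7 also plans by-visit summaries and a repeated-measures model. This stands and limits the weight of the point.

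**Conclusion.** The concern holds conditionally. As literally written, the protocol lets assessment frequency follow a toxicity-related event after randomisation and uses an endpoint that is sensitive to that frequency. With identical symptoms, the artefactual hazard ratio against the arm with more delays is about 1.02 to 1.06 for 15% vs 5% delays per cycle, and 1.03 to 1.11 for 30% vs 10%.

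These sizes rest on assumed delay rates, numbers of extra forms and score variability, and on delays unrelated to symptoms. If sites do not use the option, or delays are equal, there is no bias. PFS, OS and the success criterion are untouched. The extra forms may also affect the two-assessment improvement rule; that was not calculated and its direction is unknown.

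**What to change.** In Section 9.4.1.3, state that time to deterioration uses only assessments within the scheduled windows of Tables 1 and 2 (±7 days on treatment) and, for consistency, apply the same rule to improvement rate and best response. An unscheduled form should be used only to replace a missing scheduled one when it falls in that window, and otherwise listed. An analysis of all forms can be kept as a sensitivity analysis. Collection under Section 1.1 and footnote u need not change.

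The cost is small: a few unscheduled questionnaires leave the main PRO analysis. Some genuine worsening during a delay will be dated at the next scheduled visit, or missed if it resolves before then. That loss follows the same rule in both arms, and the all-forms sensitivity analysis would show it.
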